#### 10.5.3 Safety analyses and parameters

The safety evaluation will be based mainly on frequency of adverse events (AEs), number of patients with laboratory values outside the reference ranges, and number of patients with clinically significant changes in ECGs. Other safety data (for example, vital signs and special tests) will be considered when appropriate.

#### 10.5.3.1 Adverse events

All AEs recorded during the study will be summarized. The incidence of treatment-emergent AEs (new or worsening from baseline) will be summarized by system organ class, severity (based on CTCAE grade), type of AE, and relationship to the study drug. Deaths that may be reported as SAEs and non-fatal serious adverse events will be listed by patient and organized in the table by type of AE.

### 10.5.3.2 Laboratory abnormalities

All laboratory values will be converted in SI units and the severity grade will be calculated using the appropriate Common Toxicity Criteria (CTC).

The frequency of laboratory abnormalities will be shown by parameter and study day. Considerably abnormal laboratory values (new or worsening from baseline based on CTC grade) will be summarized by laboratory parameter. The tables will show the comparison between the baseline laboratory result (CTC grade) and the worst result (expressed in CTC grade) during the study. Patients with abnormal laboratory values will be mentioned and values outside the normal range will be flagged. A separate list of CTC grade 3 or 4 laboratory abnormalities will also be provided.

## 10.5.3.3 Other safety data

Weight, height, and vital signs will be summarized in each period, using descriptive statistics (N, mean, standard deviation, median, minimum, and maximum).

Physical examination abnormalities, ECOG performance status, radiology tests, ECGs, MRIs, and visual evaluations will be identified and listed.

## 10.5.4 Tolerability

Dose decreases and AEs related to the study drug, e.g., gastrointestinal disorders, glucose metabolic disorders, cardiac dysfunctions, laboratory abnormalities, infections, and injection site reactions, will be summarized by presenting counts and percentages for the safety population.

## 10.6 Sample Size Calculation

This study is a proof of concept. The sample size of 19 evaluable patients was selected without taking statistical power into account. The response rate (proportion of patients with tumor volume decrease  $\geq 20\%$ ) of at least 10% is considered clinically significant for this patient population. Table 10.1 presents the probability that there are two or more responders for the many assumed response rates. If the actual response rate is 10%, the probability of obtaining two or more responders among the 19 patients is 58%. In this study, a 90% CI will also be obtained. Table 10.2 presents the exact 90% CI when 2 - 6 among 19 patients respond to treatment. Considering that the study dropout rate is 20%, 23 patients will be enrolled in order to obtain the 19 evaluable patients for the final analysis.

Table 10.1: Probability of  $\geq 2$  responders in a 19 patient sample.

assumed p	0.05	0.10	0.15	0.20	0.25	0.30	
$P(X \ge 2)$	25%	58%	80%	92%	97%	99%	
X is assumed to have a binomial distribution with p probability							

Table 10.2: Resulting 90% CI for different numbers of responders

Responders / n	Lower confidence interval	Upper limit of the confidence interval
2 / 19	1.9%	29.6%
3 / 19	4.4%	35.9%
4 / 19	7.5%	41.9%
5 / 19	11%	47.6%
6 / 19	14.7%	53%

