	The primary efficacy variable is the proportion of patients with NFPA reaching tumor response, defined as tumor volume decrease of at least 20% after 24 weeks of treatment with pasireotide LAR. The response rate will be summarized in terms of incidence rates and the 90% confidence interval at the end of the Main period of the study (Week 24). The same analysis will be repeated for the PPS population.  Secondary Objectives: All secondary efficacy analyses will be based in the full analysis set (FAS). The safety analysis set will be used for all safety analyses. The secondary efficacy endpoints are described in section 3.3.2.  Safety:
	The safety evaluation will be based mainly on the frequency of adverse events (AEs) and on the number of patients with laboratory values outside the reference ranges. Other safety data, such as physical examination, weight, height, vital signs, ECOG performance status, radiology tests, ECGs, MRIs, and visual evaluations, will be summarized as appropriate.

 	,				
	Calculation of the Sample Size:  The sample size of 19 patients has been selected regardless of statistical power. A response rate (tumor volume decrease ≥ 20%) of at least 10% of patients is considered clinically significant for this population. If the actual response rate is 10%, the probability of obtaining two or more responders among the 16 patients is 58%. In this study, the exact 90% CI will also be obtained. The table below shows the exact 90% CI when 2 - 6 patients, among the 19 patients, respond. Considering a drop-out rate of 20%, 23 patients will be enrolled in order to obtain 19 evaluable patients for the final analysis.				
	Responders / n	Responders / n Lower confidence limi			
	2/19	2/19 1.9% 3/19 4.4%		29.6%	
	3/19			35.9%	
	4/19	7.5%		41.9%	
	5/19	11%		47.6%	
	6/19	14.7%	)	53%	
Planned Dates	FPFV: August 2011	LF	PFV: April 2	2012	
Number of patients, sites, and location of the	Total number of patients: Number of sites: 13	23			

Location of the sites: Brazil

sites

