## 10.4.3 Control of missing values / censoring / discontinuations

A patient whose tumor volume evaluation at the beginning of the study (Screening Period, baseline data) is missing will not be considered for efficacy evaluations. Only patients with baseline evaluation and at least one later evaluation will be considered for statistical analysis. All analyses will be performed with the data observed, i.e. the primary analysis (Week 24) will only be based on data from patients with both baseline and Week 24 tumor volume evaluation.

The primary endpoint analyses will be based on the cases seen, as the population is treatmentnaïve (also not having undergone surgery), and 24 weeks of treatment are expected to be necessary before a significant effect is evaluated.

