5.6 SAMPLE SIZE RATIONAL

This is a proof of concept study. The sample size of 19 evaluable patients was selected without regard for statistical power. A response rate (proportion of patients with tumor volume reduction ≥ 20%) of at least 10% is considered clinically meaningful for this patient population. **Table A 3**, presents for various assumed response rates the probability of having two or more responders. If the true response rate is 10%, the probability of getting two or more responders out of 19 patients is 58%. In this trial the 90% CI will also be obtained. **Table A 4**, presents the exact 90% CI when 2-6 patients respond out of the 19 patients. Considering the dropout of 20%, we will enrol 23 patients to get 19 evaluable patients for final analysis.

Table A 3: Probability of getting ≥ 2 response in a sample of 19 patients

Assumed p	0.05	0.10	0.15	0.20	0.25	0.30
P(X ≥ 2)	25%	58%	80%	92%	97%	99%
X is assumed to have	binomial distri	bution with	probability	р		

Table A 4: Resulting 90% CIs for various number of observed responders

Responders/n	Lower confidence limit	Upper confidence limitl
2/19	1.9%	29.6%
3/19	4.4%	35.9%
4/19	7.5%	41.9%
5/19	11%	47.6%
6/19	14.7%	53%

6 Study Results

The study results are presented in Appendix 1: Statistical Tables – Core study phase.

The extension study results are presented in Appendix 2: Statistical Tables – Extension study.

7 Clarifications to the study protocol

The following clarifications to the study protocol were considered on this SAP:

- Clarification of statistical analysis for time to response and baseline characteristics
- Definition of treatment-emergent adverse events
- Definition of comparative analysis of hormonal parameters
- Confidence interval of 95% instead of 90% due to the standard approach in clinical epidemiology

Any deviations from methodology/definitions/analysis described on this SAP should be previously accepted by the sponsor and documented (together with reasoning, if relevant) in the statistical analysis report.

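### The synopsis attaches the 58% probability to 16 patients instead of 19; separately, and minor, 23 enrolled with 20% dropout gives 18.4 expected evaluable patients, not 19

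*Protocol*

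**What the plan says.** The sample-size rationale appears in three places: the protocol synopsis (Calculation of the Sample Size, under statistical methods), protocol section 10.6 and SAP section 5.6. None is a power calculation. Section 10.6 says "The sample size of 19 evaluable patients was selected without taking statistical power into account" and the synopsis says "The sample size of 19 patients has been selected regardless of statistical power". The rationale consists of the chance of seeing at least two responders and a table of exact 90% confidence intervals for 2 to 6 responders out of 19.

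- **Probability, protocol body.** "If the actual response rate is 10%, the probability of obtaining two or more responders among the 19 patients is 58" per cent. The note to Table 10.1 gives the model: "X is assumed to have a binomial distribution with p probability". SAP section 5.6 and its Table A 3 give the same figure for 19.
- **Probability, synopsis.** "the probability of obtaining two or more responders among the 16 patients is 58" per cent. The same paragraph opens with 19 patients, tabulates responders out of 19 and ends with 19 evaluable.
- **Enrolment.** Section 10.6: "Considering that the study dropout rate is 20%, 23 patients will be enrolled in order to obtain the 19 evaluable patients". SAP section 5.6: "Considering the dropout of 20%, we will enrol 23 patients to get 19 evaluable patients for final analysis". The synopsis gives the same three numbers.
- **Who counts.** Protocol section 10.4.3 says "the primary analysis (Week 24) will only be based on data from patients with both baseline and Week 24 tumor volume evaluation", and SAP section 5.4.3 agrees. Last observation carried forward is used only as a sensitivity analysis (protocol 10.4.4, SAP 5.4.4).

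**The concern.** The synopsis pairs one probability with a sample size that appears nowhere else in the rationale. Either the 58% or the 16 must be wrong. Someone who reads only the synopsis cannot tell which, and cannot reproduce the figure.

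The enrolment sentence does not follow from its own inputs: removing 20% of 23 does not leave 19. This would be harmless if every treated patient were in the primary denominator. Here the primary analysis uses observed cases, so a patient without a Week 24 volume leaves both numerator and denominator. With no hypothesis test and no power target, this short section is the only quantitative support for the trial's size, so its figures should agree with one another.

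**Working it through.** **Inputs.** Target evaluable n = 19, dropout d = 20%, enrolled N = 23, response rate p = 10%, binomial model (protocol 10.6, SAP 5.6); n = 16 (synopsis).

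**1. Reproduce the plan's own figure.** P(X >= 2) = 1 - 0.9^n - n x 0.1 x 0.9^(n-1).

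- n = 19: 1 - 0.1351 - 0.2852 = 0.580. This is the stated 58%.
- The other entries of Table 10.1 also reproduce at n = 19: 0.245, 0.802, 0.917, 0.969 and 0.990 for p = 0.05, 0.15, 0.20, 0.25 and 0.30.
- All five Clopper-Pearson 90% intervals in Table 10.2 reproduce at n = 19, from 1.9-29.6% for 2 responders to 14.7-53.0% for 6.

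**2. The synopsis figure.** n = 16: 1 - 0.1853 - 0.3294 = 0.485. The probability for 16 patients is 48.5%, so the synopsis is out by 58.0 - 48.5 = 9.5 percentage points. Only n = 19 returns 58%.

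**3. The enrolment figure.**

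- Expected evaluable: N x (1 - d) = 23 x 0.8 = 18.4.
- Enrolment needed for 19 on expectation: n / (1 - d) = 19 / 0.8 = 23.75, so 24 (24 x 0.8 = 19.2).
- Dropout at which 23 leaves 19: 1 - 19/23 = 4/23 = 17.4%. Five dropouts (5/23 = 21.7%) leave 18.
- 19 x 1.2 = 22.8 rounds up to 23, so multiplying by 1 + d would explain the stated number. The documents do not show the step, so this is an inference.

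**4. What the shortfall costs.** Take each patient as evaluable with probability 0.8, independently of response.

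| Quantity | 23 enrolled | 24 enrolled |
|---|---|---|
| Expected evaluable | 18.4 | 19.2 |
| P(at least 19 evaluable) | 50% | 66% |
| P(at least 2 evaluable responders), p = 10% | 55.9% | 58.3% |

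The last row uses 0.8 x 0.1 = 0.08 as the chance that an enrolled patient is an evaluable responder. For N = 23 this gives 1 - 0.92^23 - 23 x 0.08 x 0.92^22 = 0.559. With exactly 18 evaluable the probability is 1 - 0.1501 - 0.3002 = 0.550, and the exact 90% interval for 2 responders is 2.0-31.0% instead of 1.9-29.6%.

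**The case against.** The strongest case on the other side is that nothing in the trial turns on this, and most of that case stands.

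- The enrolment gap is 0.6 of an expected patient, or one enrolled patient. Under Bin(23, 0.8), 19 is both the median and the single most likely evaluable number (20.4%, against 19.4% for 18). Four or five dropouts out of 23 could each be rounded to 20%.
- The 50% chance of at least 19 evaluable sounds poor on its own, but the conventional 24 gives only 66%. Inflating for expected dropout never guarantees the target.
- The study is described as a proof of concept, with size chosen without regard to power. There is no success threshold to miss, and the reported interval will use the n actually observed.
- Dropping out need not mean being unevaluable. Protocol section 6.4.4 brings patients who stop early back for the Visit 10 evaluations, which include an MRI. The documents do not say whether such a scan counts as Week 24, so a one-for-one loss is an assumption.

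A reader might infer that the 58% and the two tables are wrong, or that the trial fails to deliver its design and must enrol 24. The documents do not support either reading. The 58% and both tables are stated for 19 patients and are exact for 19, and no target exists that a drop to about 56% would breach.

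The objection does not rescue the two sentences themselves. The synopsis probability is false for 16 patients under any reading, and 20% of 23 is 4.6 patients, which does not leave 19.

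**Conclusion.** The point holds as two corrections of unequal weight. The clearer one is the synopsis: 58% belongs to 19 patients, while 16 patients would give 48.5%. Since 19 is used in the rest of that paragraph, in section 10.6 and in the SAP, 16 is best read as a slip for 19.

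The minor one is the enrolment sentence in all three places. At the stated 20% dropout the expected evaluable number is 18.4, and the chance of at least two evaluable responders at a 10% rate is about 56%, roughly 2 points below the quoted 58% (55.0%, or 3 points lower, if exactly 18 are evaluable). These figures assume that a dropout has no usable Week 24 volume and that dropout is unrelated to response. No planned analysis or conclusion changes.

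**What to change.** 1. In the synopsis, change 16 to 19 in the probability statement.
2. In the synopsis, protocol section 10.6 and SAP section 5.6, make the enrolment sentence consistent in one of two ways:
   - state that 23 enrolled gives 19 evaluable at about 17% dropout (4 of 23), which leaves every other figure as it is; or
   - keep 20% and state that about 18 evaluable patients are expected, with a probability of about 55 to 56% of at least two responders at a 10% rate.

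Tables 10.1 and 10.2, SAP Tables A 3 and A 4 and the synopsis interval table are correct for n = 19 and can stay. The cost is a few words in three places. The second option makes the quoted probability slightly less favourable. Neither option changes enrolment or the analysis.

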# 11 Administrative procedures

# 11.1 Enrollment compliance

When all inclusion / exclusion criteria are met and a patient is qualified to enter the study and when all information is entered into the eCRF, enrollment will be allowed. This will allow enrollment to be properly monitored and will ensure that the populations with each type of tumor are appropriately represented in the study.

# 11.2 Ethic and regulatory compliance

This clinical study was designed and must be implemented and reported according to the protocol, the Harmonized Tripartite Guideline for ICH Good Clinical Practice, the applicable local regulations (including European Resolution 2001/20/EC and U.S. Code of Federal Rules Title 21), and the ethical principles established in the Declaration of Helsinki and the Brazilian legislation.

# 11.3 Investigator's and REC's responsibilities

The protocol and the proposed informed consent form must have been reviewed and approved by a duly established Research Ethics Committee (REC) before the start of the study. A signed and dated statement that the protocol and informed consent form were approved by the REC must be submitted to Novartis before the start of the study. Before the start of the study, the investigator must sign a protocol signature page confirming his/her agreement to conduct the study according to these documents and all instructions and procedures found in this protocol, in addition to providing access to all pertaining data and records to Novartis monitors, auditors, Novartis Clinical Quality Assurance representatives, Novartis designees, RECs, and regulatory authorities, as required.

#### 11.4 Informed Consent Form

Eligible patients may only be enrolled in the study after providing the written informed consent (witnessed, whenever required by law or regulation), approved by the REC or, if unable to do it, after this consent is provided by the patient's legally acceptable representative.

In cases in which the patient's representative provides the consent, the patient must be informed about the study as far as possible, considering his/her understanding. If the patient is able to understand, he/she must indicate his/her consent by personally signing and dating the written informed consent form or a separate consent form. The informed consent must be obtained before the performance of any study-specific procedures (i.e., all procedures described in the protocol). The process of obtaining the informed consent must be documented in the patient's source-documents.

Novartis will provide the investigators, in a separate document, with a proposed informed consent form following ICH GCP guidelines and regulatory requirements and considered appropriate for this study. Any changes to the proposed consent form suggested by the investigator must be approved by Novartis before submission to the REC, and a copy of the approved version must be provided to the Novartis monitor after approval by the REC.

Women of childbearing potential must be informed that the use of the study drug may involve unknown risks to the fetus in case of pregnancy during the study, and must agree that, in order to participate in the study, they must meet the contraceptive requirement throughout the study. In case of any doubt that the patient will reliably comply with the treatment, he/she must not be enrolled in the study.

#### 11.5 Protocol amendments

Any change or addition to the protocol may be performed only by means of a written protocol amendment, which must be approved by Novartis, Health Authorities, whenever required, and by the REC. Only amendments required for the safety of patients may be implemented before approval by the REC. In spite of the need for formal approval for protocol amendments, the investigator is expected to take any immediate action required for the safety of any patient enrolled in this study, even if this action represents a protocol deviation. In such cases, Novartis must be notified about such action and the REC of the study site must be informed within 10 business days.

## 11.5.1 History of amendments

Amendment 1 extends the treatment schedule for patients from week 24 to week 96.

For the purpose of a reference for long-term safety and efficacy evaluation of pasireotide LAR treatment, patients benefiting from the treatment with this medication according to the evaluation by the physician in charge will be offered the opportunity to enter a 72-week extension period.

- Protocol amendment 2 includes additional liver safety measurements as a result of an internal medical review of the pasireotide studies, on visits Core - V3 (D20), V4 (D28), V4L (D48), and V5 (D56);
- Extension E2 (D28), E3 (D48), E4 (D56), E4L (D76), and E5 (D84).

# 11.6 Discontinuation of the study

Participation in this study is voluntary. Research subjects may withdraw their consent. The investigator may discontinue the participation of any research subject in this study, at any time, if considered as in his/her best interest.

Novartis Biociências S. A. may discontinue the study at any time, if anything that might compromise the safety of research subjects is found. If this happens, the Hospital Ethics Committee must approve the reasons prior to discontinuation.

# 11.7 Supply and new supply, storage of the drug, and traceability / accountability of the study drug

Study drugs must be received by a designee at the study site, handled and stored safely and appropriately, and kept in a safe place, with access restricted only to the investigator and his/her designees. Upon receipt, pasireotide LAR must be stored according to the instructions specified in the drugs labels. Clinical supplies must be dispensed only according to the protocol.

Medication labels will be written in local language and will follow Brazilian legal requirements. These labels will include the storage conditions for the drug, but not information on the patient.

The investigator must keep an accurate record of the shipment and dispensing of the study drug in a drug accountability log. Drug accountability will be observed by the field monitor during visits to the site and upon completion of the study. The site staff will be asked to return all unused study drug and packages at the end of the study or at the time of discontinuation of the study drug.

At the end of the study and as appropriate throughout the study, the investigator will return all study drug, packages, drug labels used and unused, and a copy of the completed drug accountability log, to the Novartis monitor or to the Novartis address provided in the investigator's binder at each site.

# 12 Protocol compliance

The investigators agree to dedicate due diligence to avoid protocol deviations. The investigator must not, under any circumstances, contact Novartis or its representatives, if any, monitoring the study to request approval for a protocol deviation, as no authorized deviation is allowed. If the investigator considers that a protocol deviation would improve the study conduction, it must be considered as a protocol amendment and, unless this amendment is agreed upon by Novartis and approved by the REC, it cannot be implemented. All significant protocol deviations will be recorded and reported in the eCSR.

# 13 Publication policy

Any formal presentation or publication of the study data will be considered as a joint publication by the investigator(s) and Novartis team. Authorship will be determined by mutual agreement, based on the number of patients enrolled. For multicenter studies, it is mandatory that the first publication be based on data from all sites, analyzed as established in the protocol by Novartis statisticians, and not by the investigators.

The investigators participating in multicenter studies agree not to submit data from one site or small groups of sites before complete publication, unless formally approved by all investigators and Novartis.

Novartis must receive copies of any communication before publication (at least 20 business days for abstracts and oral presentations and 45 business days for submission to journals). Novartis will review the communications for accuracy (thus avoiding potential discrepancies regarding the submission to health authorities), verify that confidential information is not unadvertedly disclosed, and provide any relevant supplementary information.

The investigator may be asked to sign the clinical study report, if required to be used in a registration submission to health authorities in some countries. For multicenter studies, only the principal investigator appointed by Novartis at the beginning of the study must provide any signature required.

